1) The Comprehensive Health Program at Columbia University/NewYork-Presbyterian Hospital provides primary care, HIV specialty care and care coordination services to over 2,000 PLWH. 95% of individuals are of either Black or Latino background and women represent half of the overall population. In addition, the program has 28 direct clinical providers, 8 social workers, and 10 additional care coordinators. Of note, [name] (Co-I) is an attending physician at the Clinic.

2) AIDS Service Center (ASC) is a community based organization for PLWH and persons at risk for HIV. ASC has more than 90 staff, 85 peer interns, and more than 1,800 clients who come for services each year. In addition, another 18,000 people are reached through the peer education and community outreach initiatives of ASC. Given our past experience and success in recruiting participants and using the recruitment strategies described above, we are confident that we will be able to recruit the number of participants needed to conduct the study within the study timeframe. See details in Section A.3.3. Preliminary Work.

STATISTICAL PROCEDURES

D.4. Power and Sample Size.

We will recruit 200 individuals and have greater than 80% power to detect a less than 10% difference in adherence to ART medications between the Wise App and the control group. We assume a 25% attrition rate by the end of trial for both arms. The power calculations are based on the analysis of main outcome, ART adherence. All calculations are based on 2-sided test with alpha at 0.05 level. Our calculations are based on the assumption that each person is on a once daily regimen and the adherence rate is $\leq 80\%$ at baseline.

Many of our participants will be on regimens that are two or three times per day which will provide greater power for our study since we have a greater number of measurements (e.g., 180 for once daily vs. 360 for twice daily regimen). To illustrate, if the adherence rate for the control group does not change, we will have 90.7% power to detect a 6% increase in ART adherence for the intervention group (e.g., from 80% to 86% at

Table 2. Comparison of Intervention vs. Control Group

	Intervention	Control
The Wise App • Medication reminder • Step Goal reminder	✓ ✓	✓
CleverCap™ Lite dispenser	✓	✓

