the end of the trial). If the adherence rate for the control group increases 4%, from 80% to 84% at the end of the trial, we will have 88.6% power to detect a 5% difference in adherence between the intervention and control group. In this case, the intervention group's adherence rate increased an additional 5% (or $4\% + 5\% = 9\%$) from 80% to 89% at the end of the trial.

D.5. Baseline Screening and Assessment.

Potential study participants will complete a phone screening that assesses eligibility. If eligible, participants will attend a baseline session described below.

D.6. Randomization.

Study participants will be randomized (1:1) to Wise App intervention or control arm. We will use a variable permuted randomized block design⁶⁸ where the block size itself is randomly selected (i.e., blocks of four to eight). The advantage of the permuted block design is that treatment assignment is pre-determined before the trial begins and then assignment remains static throughout the course of the trial⁶⁹. Participants will be randomized based on the use of computer-generated random numbers at baseline. The randomization database will be stored on a password protected computer at Columbia University and will only be accessible to [name].

D.7. Procedures.

Upon enrollment in the study, participants will come to the study site, Columbia University School of Nursing to complete consent forms. Following informed consent, study participants will complete a number of baseline questionnaires including socio-demographic characteristics, physical health measurements, behavioral data, health status and social desirability (See Table 3)⁷⁰. Survey instruments will be collected through Qualtrics, a secure, Web-based application designed to support data capture for research studies, providing an intuitive interface, audit trails, and automated export. Qualtrics is a free service offered through Columbia University Medical Center.

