We will also use additional measurements of medication adherence to validate the findings from the CleverCap™ Lite dispenser. We will do blood draws at baseline, 3 and 6 months to measure CD4 and viral load data on each study participant; alternatively, participants will be given the option of providing recent lab results of their CD4 and viral load data. The blood draw at baseline will also be tested for genotyping, GSA chip and qPCR, Hormone blood levels (Estrogen and FSH), and cytokine blood levels (IL-1 β , IL-2, IL-4, IL-6, IL-8, IL-10, IL-13, TNF α , and CRP). The genotyping with GSA chip and qPCR, cytokine blood level and CRP, and hormone blood tests will only be collected once during the course of the study, at Baseline or at the 6-month follow-up if not completed at Baseline. The genotyping, GSA chip and qPCR will be performed by the Feinstein Institute for Medical Research at Northwell Health. We will also ask participants to complete the Center for Adherence Support Evaluation (CASE) Adherence Index, a simple composite measure of self-reported antiretroviral therapy (ART) adherence⁸¹. The CASE Adherence Index consists of three unique adherence questions. Past research has shown that the CASE Adherence Index correlated strongly with the three-day self-reported adherence data ($p<0.001$) and was more strongly associated with HIV outcomes, including a 1-log decline in HIV RNA level (maximum OR=2.34; $p<0.05$), HIV RNA<400 copies/ml (maximum OR=2.33; $p<0.05$) and performed as well as the three-day self-report when predicting CD4 count status. The CASE Adherence Index is an easy to administer instrument that provides an alternative method for assessing ART adherence in clinical settings. Items are scored such that higher values indicate better adherence, and the maximum total score is 16. Scores of 11 or higher on this index indicate good adherence (Cronbach's $\alpha=0.79$)⁸⁶.

Our primary outcome is ART adherence. The CleverCap™ Lite dispenser is our objective measure of ART adherence and the CASE Adherence index as a subjective measure. We are including the subjective measure since there is potential bias in that participants' in the control group may not use the device or may not use the device for the entire study period.

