We will assess for contamination between the study groups at the end of the trial by asking control group participants whether they had used any HIV or medication related apps in the past 6 months. In addition, participants will return at 3 and 6 months to complete the remainder of the measures listed in Table 3 and included in the Appendix. We will also collect data on app use through automated log files so there will not be response burden associated with this measure.

Secondary Outcome Measures: Our measures are listed in Table 3 and included in the Appendix.

D.9. Data Analysis.

We will use intention-to-treat principles for the primary outcome analysis. Intention to treat implies all subjects are considered in analyses. The outcome variable y_{-i} will be the total number of times the CleverCap™ Lite dispenser is opened at day t (from day 1 to day 180) for person i , so y_{-i} follows binomial distribution with parameter of p_{-i} and n where p is probability of taking medication (adherence rate) and n is number of medications to take each day. We use a generalized linear mixed model (GLMM) with logit link function to analyze adherence rate. The basic form of the model is: $\log(p_{-i}/(1-p_{-i})) = \beta_0 + \beta_1 t + \beta_2 t \times \text{INT} + \mu_{-i}$. In the model, μ_{-i} is person level random effect and follows normal distribution. This model is also called individual growth model. Independent variable INT is an indicator for intervention group (INT=1 for the intervention group and INT=0 for the control group). Regression parameter β_1 is change in adherence rate for the control group and β_2 is the difference in change in adherence rate between the intervention group and the control group.

This model can include personal level factors as covariates so we can test for potential confounding by covariates (i.e., age, gender, and health literacy) in this model and inspecting for changes in the point estimate of the relation between study group and adherence.

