We will use GLMM for analyzing secondary outcomes. In our analysis of the surveys related to the SDT framework, the variable time (t) will be at 3 time points (baseline, 3 month, and 6 month) and the link function will be identified for continuous outcomes. In the analysis of app use, the unit of analysis will be at daily level for each participant, and system use will be analyzed using a GMMM with log link function (Poisson model). For the analysis of CD4 and viral load, we will analyze difference-in-difference using GLMM with identity or log link function when these variables are treated as continuous outcomes. Viral load will also be treated as a binary outcome (detectable vs. undetectable) and analyses of viral suppression will use the GLMM with logit link. In a secondary “as treated” analyses, missing adherence and viral load data will be ignored. The genotype analysis will be run by the Feinstein Institute for Medical Research at Northwell Health. Finally, we will assess the relationship between adherence (independent variable) and virologic suppression (dependent variable) using GLMM logistic regression and including missing viral load as detectable. This model will include personal level factors as covariates so we can test for potential confounding by covariates (i.e., age, gender, and health literacy) in this model and inspecting for changes in the point estimate of the relation between study group and adherence.

E. Aim 2b: Assess the acceptability of the CleverCap™ dispenser through In-depth interviews, which will focus on the individual experience of PLWH with the device.

E.1. Sample. At the 3-month follow-up visit, semi-structured in-depth interviews will take place with participants in the intervention group. These participants will be the same participants from the intervention study arm, if they choose to participate (N=100)

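### The primary GLMM as printed has only a random intercept, so its 5% test of the time-by-arm slope is anti-conservative if trends vary between people, lapses cluster, or missing days count as non-openings

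*Combined protocol and SAP*

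**What the plan says.** Section D.9 (Data Analysis) models the daily number of dispenser openings, day 1 to day 180, as binomial with a logit link. The linear predictor is β0 + β1·t + β2·t×INT + μ. The text says that μ "is person level random effect and follows normal distribution. This model is also called individual growth model". β2 is the difference between arms in the change in adherence. Covariates are the only extension mentioned.

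Section D.4 fixes the level: "All calculations are based on 2-sided test with alpha at 0.05 level". It also expects losses: "We assume a 25% attrition rate by the end of trial for both arms". Two power figures follow: "we will have 90.7% power to detect a 6% increase in ART adherence for the intervention group", and, if control adherence rises from 80% to 84%, "we will have 88.6% power to detect a 5% difference in adherence between the intervention and control group".

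On days without data, D.9 says of the primary analysis only that "Intention to treat implies all subjects are considered in analyses". In a secondary as-treated analysis, "missing adherence and viral load data will be ignored". Section D.8 warns that participants in "the control group may not use the device or may not use the device for the entire study period".

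**The concern.** β2 is a difference in slopes. A random intercept absorbs differences between people in their level of adherence, but not differences in how adherence changes over six months. Given the intercept, the model treats a person's 180 days as independent. Three departures break this:

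- trends that differ between people in the same arm;
- missed doses that come in runs;
- days after dropout scored as non-openings, so that each dropout adds a long run of zeros.

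In each case the model-based standard error of β2 is too small. The p-value and confidence interval for β2 are the primary result, so the stated two-sided 0.05 level would not hold. The plan neither states nor checks the conditions under which it does.

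The departures are plausible on the protocol's own account. The rationale section says that engagement with mHealth tools falls over time and justifies real-time monitoring by the need to catch lapses. If some control participants stop using the device and others do not, trends within that arm differ.

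**Working it through.** **Inputs from the documents.** 100 per arm (Table 1), 180 days (D.9), two-sided α = 0.05, 25% attrition in both arms, once-daily dosing, 80% adherence (D.4).

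**Assumed inputs.** Random-intercept SD 1, with 0.5 and 2 as sensitivity values. Random-slope SD τ on the logit scale over six months, from 0 to 1. Each person drops out with probability 0.25 on a uniformly random day, regardless of arm.

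**The plan's own power figures.** They cannot be rebuilt, because no variance or intraclass correlation (ICC) is given. With 75 completers per arm:

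- One binary outcome per person gives 16% and 14% power for the two examples.
- 180 independent days give about 100%.
- With design effect 1 + 179×ICC, the stated 90.7% needs an ICC of 0.084 and the stated 88.6% needs 0.075.
- The printed random-intercept model gives about 99% in both examples for intercept SDs from 0.5 to 2.

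**Hand check of the mechanism.** With 100 per arm, Var(β2) ≈ SE² + 2τ²/100, where SE is what the model reports. At τ = 0.5 this gives √(0.098² + 2×0.25/100) = √0.0146 = 0.121. The false-positive rate is 2[1 − Φ(1.96×0.098/0.121)] = 2[1 − Φ(1.59)], about 11%.

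**Reading A: dropout days missing.** The printed model was fitted by maximum likelihood to data with no arm difference, 1000 runs per scenario. The Monte Carlo SE is about 0.7 points near 5% and 1.4 near 28%.

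| τ | Day-180 adherence at ±1 SD around 80% | False positives, printed model |
|---|---|---|
| 0 | 80% | 4.4% |
| 0.25 | 76–84% | 6.7% |
| 0.5 | 71–87% | 13.8% |
| 1.0 | 60–92% | 27.7% |

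The reported SE against the actual SD of β2 was 0.098 against 0.129 at τ = 0.5, and 0.099 against 0.178 at τ = 1.0. Putting these into the formula, 1.96×0.098/0.129 = 1.49 gives about 14%, and 1.96×0.099/0.178 = 1.09 gives about 28%, in line with the table. A separately coded simulation (600 runs, no dropout) gave 5.5%, 6.2%, 11.0% and 28.7%.

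**Runs of lapses.** In the second simulation, with equal slopes and no dropout, lag-1 correlations of 0.2, 0.4 and 0.6 gave 9.8%, 18.2% and 31.0%.

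**Reading B: dropout days scored as non-openings.** Slopes are equal and lapses otherwise independent.

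- 25% attrition: 60.8%, with reported SE 0.091 against actual SD 0.351. Check: 1.96×0.091/0.351 = 0.51, about 61%.
- 10% attrition: 44.7%. 5% attrition: 33.4%.
- At 25% attrition, 59–63% for intercept SD 0.5 or 2, and 57% if all dropout falls after day 90.
- The second simulation gave 63% at 25% and 51% at 10%. It set 80% as the population average rather than the value for a person with the average intercept, which may explain the gap at 10%.

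**Same fits, participant-clustered SEs.** 4.1–6.0% in all 15 null scenarios, and 4.2–6.2% in the second simulation. A further 600-run check at τ = 0.5 gave 6.7%, with Monte Carlo SE about 1 point.

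**Power with clustered SEs.** The two D.4 examples are almost the same effect on the logit scale: logit 0.86 − logit 0.80 = 1.815 − 1.386 = 0.429, and logit 0.89 − logit 0.84 = 2.091 − 1.658 = 0.433. Under reading A both have 99%, 96%, 89% and 60% power at τ = 0, 0.25, 0.5 and 1.0. Under reading B at 25% attrition both have about 10% (500 runs each).

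**The case against.** **The model may be under-described rather than wrong.** D.9 presents the equation as a basic form, the growth-model label often implies a random slope, and the formula's subscripts are damaged in the extracted text. D.4's power figures sit well below the 99% that the printed model gives and close to the 89% found at slope SD 0.5, so D.4 may already have allowed for varying trends. This stands as a possibility. It does not remove the point, because one person-level term is all that the prose specifies, and an analyst following it would fit a random intercept.

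**The size depends on assumptions.** This also stands. No document figure selects a slope SD or a serial correlation, and at slope SD 0.25 the inflation is minor.

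**Reading B is not a stated rule.** Considering all subjects is a statement about people, not days, and a likelihood analysis of the available days satisfies it. Where the plan wants missing data counted as failure, it says so, and only for viral load. Against that, ignoring missing adherence is named only for the secondary analysis, which suggests something else for the primary one. The 61% is therefore the consequence of one open reading, and it is as much a missing-data issue as a standard-error issue.

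**D.8 speaks of bias between arms, not of varying slopes within an arm.** Correct. It supports the plausibility of differing trends and no more.

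**Clustered SEs have not been shown to be better than a random slope.** No random-slope model was fitted, so the two were not compared. A random slope addresses differing trends but need not handle runs of lapses.

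**Conclusion.** The concern holds. As printed, D.9 gives a valid 5% test of β2 only if trends are equal within each arm, lapses are independent given the intercept, and days without data are left out. Otherwise the test is anti-conservative. With dropout days missing, the false-positive rate ranges from no inflation at slope SD 0 to about 14% at 0.5 and 28% at 1.0. Runs of lapses alone took it to between 10% and 31% over the correlations tried. Counting dropout days as non-openings takes it to about 61% at the plan's own attrition rate.

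These sizes rest on assumed variance components and on dropout unrelated to arm or adherence, so confidence in the magnitude is medium. D.4's power figures are not shown to be wrong, but their variance basis is undocumented. This should be fixed before analysis.

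**What to change.** Add to D.9:

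1. The primary test and confidence interval for β2 use participant-clustered (sandwich) standard errors.
2. An explicit rule on whether days without data, after dropout or device non-use, are missing or count as non-openings.

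A person-level random slope for t would match the growth-model label and is an optional addition. In D.4, state the variance components and missing-day rule behind 90.7% and 88.6%, and recheck both figures with the clustered standard error.

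The cost is one or two sentences. If trends are equal and dropout days are missing, precision is unchanged in practice (mean SE 0.098 model-based, 0.097 clustered). If slopes vary with SD 0.5, intervals widen because the SE goes from 0.098 to 0.126. The missing-day rule has to be settled together with the standard error, since scoring dropout days as non-openings leaves about 10% power at 25% attrition. Clustering will not remove bias if device non-use differs between arms, so that needs separate handling.

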Given the dearth of useful and likeable apps ⁵⁴, the need for improving medication adherence in PLWH and the great promise that mHealth holds, we propose to test a smartphone app linked to a smart pill box called CleverCap™ Lite (The Wise App) for PLWH targeting ART adherence and guided by a rigorous and relevant theoretical framework⁵⁵. The feasibility of the Wise App is supported by data demonstrating that use of mobile devices is nearly ubiquitous in the U.S. with persons from underserved groups being more likely to own a smartphone and more likely to use a smartphone (as compared to a computer) to access the Internet. The current trial is significant in representing one of the first principled and systematic efforts to build a mHealth app intervention based on user-centered design work and linked to a smart pill box for improving health outcomes. Our proposed study, based on our empirical findings from our preliminary work ⁵⁶⁻⁶¹, uses rigorous methods and a theory-based approach ⁵⁵ to develop and test a mHealth intervention (Wise App) for improving ART adherence for PLWH.

STUDY DESIGN

The goal of this study is to test the efficacy of The Wise App for improving health outcomes (as measured by improving ART adherence) in PLWH. Our secondary outcomes are: (a) healthcare access (b) technology

acceptance (c) technology use. Table 1 presents and overview of the design, participants and data analysis plan for each aim.

Table 1. Overview of Design, Methods, Participants, and Data Analysis			
Aim	Design/Methods	Participants	Data Analysis
1	Cognitive Walkthrough, and user testing using think-aloud protocol	Cognitive Walkthrough: human-computer interaction experts (N=5); User testing: PLWH (N=30)	Quantitative and qualitative summary of heuristic violations; thematic analysis of think-aloud protocol, quantitative summary of mouse clicks, time, etc.
2	Randomized controlled design	PLWH (N=200; intervention=100, control n=100) for 6 months	Descriptive statistics; Linear regression model
2b	In-depth Interviews	PLWH (N=100; intervention group only)	Qualitative coding of in-depth interviews related to CleverCap device; thematic analysis to examine CleverCap experience and acceptability
3	Descriptive: focus groups	Focus groups: Participants in the intervention arm of the RCT (N~50)	Descriptive, thematic analysis to examine post-intervention perceptions related to The Wise App use, usefulness and impact on overall health

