Following the completion of the baseline study instruments, study participants in both arms will be given a CleverCap™ Lite dispenser and trained on how to use it, as well as a fitness tracker that will be synced to Wise App. Study participants in both arms will be trained by study team members on how to use the different features of the Wise App. Those in the intervention group will receive medication reminders while those in the control group will receive reminders about completing their step goal. Participants in both arms will be given a document that includes contact information for the project team, information about compensation, study reminders, and will also receive a telephone call from a research assistant 1 week after enrollment to assist with any technical problems with the app or the CleverCap™ Lite dispenser and biweekly thereafter.

Participants will be texted appointment reminders for study visits via Qualtrics. Hard to reach participants will also be sent scheduling reminders through the Qualtrics system and encrypted e-mails from the study's secure CUMC e-mail address.

Token of appreciation: Participants will be given \$40 at the baseline visit, \$50 + up to an extra \$25 for app challenges completed at the 3 month visit, and \$60 + up to an extra \$25 for app challenges completed at the 6 month visit (up to a total of \$200 for participation) and for providing a blood sample (or recent lab results) for viral load/ CD4 testing and completion of study questionnaires. Participants will also have the option to have the cost of their transportation to and from the study site paid for, through a ridesharing service.

D.8. Operationalization of Outcome Measures.

The primary outcome will be ART adherence, measured by the CleverCap™ dispenser. The CleverCap™ dispenser will automatically record each time a participant opens the dispenser. We will collect adherence data each day from the start to the end of trial (day 1 to 6 months), and it is a count response (number of times taking medication each day). Frequency of app use will be counted each time a participant opens the app.

Table 3. Study Measures

Tool		Measurement Time Points
Demographic Variables and Potential Confounders		
Socio-demographic characteristics	Gender, age, education, income, employment, health insurance, housing	Baseline
Behavioral Data	Use of condoms, tobacco, alcohol, substance use	Baseline, 3 and 6 months

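### The primary model has no intervention main effect, so its single treatment term can miss a benefit that arrives within about two weeks, and can test as harm when a benefit wanes to nothing

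*Combined protocol and SAP*

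**What the plan says.** D.9 takes t from day 1 to day 180 and, in plain notation, fits logit(p) = b0 + b1·t + b2·t·INT + a normal person intercept. INT is 1 for the Wise App arm and 0 for control, and it appears only inside the product with t. The coefficient numbering leaves no gap for a lost term. D.9 reads b1 as the control arm's change and says that b2 "is the difference in change in adherence rate between the intervention group and the control group". It allows person-level covariates, but gives no level, average or end-of-trial contrast for the dispenser outcome.

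On timing, D.6 says: "Participants will be randomized based on the use of computer-generated random numbers at baseline". D.7 says: "Following the completion of the baseline study instruments, study participants in both arms will be given a CleverCap™ Lite dispenser". The arms are then separated as follows: "Those in the intervention group will receive medication reminders while those in the control group will receive reminders about completing their step goal". D.8 adds: "We will collect adherence data each day from the start to the end of trial".

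D.4 illustrates power with arms that both start at 80% and separate by the end. In one case control stays at 80% and "we will have 90.7% power to detect a 6% increase in ART adherence for the intervention group". The other begins "If the adherence rate for the control group increases 4%, from 80% to 84% at the end of the trial", with the intervention arm reaching 89% and a stated power of 88.6%.

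**The concern.** The Study Design section gives the goal as "to test the efficacy of The Wise App for improving health outcomes (as measured by improving ART adherence) in PLWH". That is a question about whether adherence is higher with the app. D.9 asks a narrower one: do the arms diverge in a straight line, on the logit scale, from a common start?

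The questions coincide if the benefit builds up steadily. They part if reminders work from the first days. An early benefit is then a difference in level, present throughout the record, and the model has no parameter for it. Part is absorbed by the person intercepts and part leaks into b2. If the early benefit later fades, the fitted slope difference can be negative even though the intervention arm is at or above control every day. At stake is a primary result of no effect, or of harm, for an app that helps.

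**Working it through.** **1. The plan's own figure.** The stated 90.7% cannot be reproduced, because the documents give no between-person variance. A two-proportion test on persons, 80% vs 86%, has only 16.2% power with 75 per arm (100 less 25% attrition) and 20.2% with 100, so the figure must draw on the repeated daily records. Simulating D.9's model under linear build-up gives 100% at person SDs of 0.5, 0.75 and 1.0 logits. If personal slopes also vary (SD 0.5 or 1.0 logits per 180 days, intercept SD 0.75, robust SE), it gives 95% or 74%. The stated figure is within reach of a b2 test for build-up.

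**2. What b2 estimates when the benefit is constant.** Inputs: 180 daily records, one dose a day (D.4), 75 completers per arm, 80% vs 86%. The person SD s is assumed.

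- Put time in units of 180 days: mean 1/2, variance 1/12.
- Working variance per day near 83% adherence: v = 1/(0.83 × 0.17) = 7.09.
- Share of level information left after the person intercept: q = v/(v + 180s²).
- Effect: logit(0.86) − logit(0.80) = 0.429. Converted from marginal to person-level by the usual approximation: d = 0.429·√(1 + 0.346s²).
- Weighted least squares for D.9's three fixed terms reduces to b2 = B·d/C, with B = 180·q/2 and C = 180·(1/12 + q/4). Hence b2 = k·d, with k = 6q/(1 + 3q).
- SE(b2) = √(2v/(75·C)).
- For a linear fall from d to zero, b2 = k·d − d.

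| s | q | k | d | SE | constant: b2, power | waning to 0: b2, significantly negative |
|---|---|---|---|---|---|---|
| 0.5 | 0.136 | 0.580 | 0.447 | 0.095 | 0.259, 78% | −0.188, 51% |
| 0.75 | 0.065 | 0.328 | 0.469 | 0.103 | 0.154, 32% | −0.315, 87% |
| 1.0 | 0.038 | 0.204 | 0.498 | 0.106 | 0.102, 16% | −0.396, 96% |

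The more people differ, the more of a level effect the intercepts absorb.

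**3. Simulation of the written model.** 100 per arm, 25% dropout spread over months 1 to 5, control 80% (marginal), random intercepts only, two-sided 5%. There were 400 to 500 trials per cell, with Monte Carlo error up to about 4 to 5 points.

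| True pattern (points over control) | b2 result | SD 0.5 / 0.75 / 1.0 |
|---|---|---|
| None | significant | 4.2 / 4.6 / 4.8% |
| Linear build-up 0 to +6 | significant | 100 / 100 / 100% |
| +6 from day 1, held | significant | 77 / 33 / 16% |
| +6 by day 7, held | significant | 87 / 50 / 30% |
| +6 by day 14, held | significant | 92 / 68 / 46% |
| +6 by day 30, held | significant | 99 / 92 / 83% |
| +6 on day 1, waning to 0 | significantly negative | 56 / 87 / 95% |
| 14-day rise to +6, then to 0 | significantly negative | 36 / 70 / 84% |
| 30-day rise to +6, then to 0 | significantly negative | 16 / 42 / 59% |
| +6 on day 1, waning to +3 | significantly negative | 1 / 16 / 27% |

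The fitted day-180 difference is +3.5 / +2.1 / +1.3 points for the constant benefit (truth +6) and −3.1 / −4.6 / −5.4 for waning to zero (truth 0). Mean b2 at SD 0.75 is 0.16 and −0.31, matching step 2.

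**4. Sensitivity.** With rates set for the median person and 75 completers per arm, a steady 86% vs 80% is detected in 66 / 14 / 6 / 5% at SD 0.5 / 1 / 1.5 / 2. With varying slopes (intercept SD 0.75, slope SD 0.5 or 1.0, robust SE), the constant benefit is detected in 30% or 15%, and waning to zero is negative in 66% or 46%. Under the same slope variation, the random-intercept model's own SE for b2 rejects a true null in 15% or 33%.

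**The case against.** The plan is coherent for the pattern it illustrates. Randomisation makes equal arms at t = 0 a fair assumption, D.4 separates the arms by the end of the trial, and b2 is the most powerful of the tests considered for that pattern. This stands. A reader might infer that the common start is itself the error, or that D.4's power is refuted. Neither follows: the error is allowing only linear growth after the common start, and D.4's figures concern a benefit built up by the end.

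The worst cells are also extreme. They need the full 6 points on day 1, with either no further growth or a complete fade. A gradual rise or incomplete waning shrinks the problem considerably, so it would be wrong to say that any early benefit is missed.

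Nor do the documents predict waning. Study Purpose and Rationale reports that use of mHealth tools falls over time, but that is tool use, not pill-taking. The same paragraph says that the studies concerned still showed effects on health outcomes, and it offers gamification as the counter. Waning is possible, no more.

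Two further defences are weaker. D.9 calls its model a basic form, but the only extension it names is person-level covariates, to check confounding. CASE and viral load do have baseline readings and could expose a spurious harm signal, but they do not repair the dispenser test.

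**Conclusion.** The concern holds within limits. D.9's only treatment term cannot represent a level difference, and all the dispenser data come from the period in which such a difference could already exist. The risk of missing a real benefit applies mainly when it is in place within about two weeks and held, with a between-person SD of 0.75 logits or more. The risk of a wrong-sign result applies mainly when the benefit falls to near zero.

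The SDs are assumptions, since the documents give none, and the main cells take personal trends as equal. The structural point needs neither: it follows from the printed equation. A reader might also infer that the test is invalid. With equal personal trends it is not, since b2 rejects a true null in about 5%; its fault is that it targets one effect shape. The excess false positives arise only when personal trends differ, which is a separate reason to change the variance model.

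**What to change.** Before any comparison by arm:

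1. Add INT as a main effect in D.9.
2. Name the end-of-trial difference in adherence as the single primary test: INT + 180·b2, converted to percentage points with a confidence interval. It is the quantity D.4 illustrates.
3. Report the day 1 to 180 average difference as a pre-specified supporting estimate, and keep b2 as a secondary description of build-up or waning.
4. Add a person-level random slope for t, or use a person-clustered robust variance. The main effect alone is not enough: with slope SD 1.0, the day-180 contrast using the random-intercept SE rejected a true null in about 11% of 160 simulated trials.
5. Restate D.4's power for this contrast with an explicit between-person SD.

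The cost is a slightly larger model, new wording and some power if the benefit really does build linearly from zero: about 99.6 / 95 / 83% for the end-of-trial contrast against 100% for b2 at SD 0.5 / 0.75 / 1.0, and less if slopes vary. For a constant 6 points, the contrast gains: 99.6 / 95 / 85% against 77 / 33 / 16%.

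No single contrast is best for every pattern. If 6 points wane to 3, the end-of-trial test has 52 / 39 / 30% power and the 180-day average 99 / 84 / 71%. Under build-up, the average has only 77 / 49 / 36%. The end-of-trial contrast also still assumes a straight line within each arm on the logit scale. These are reasons to fix the choice in advance and report both.
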